We propose to retrospectively analyze the presence of chromosomal rearrangements involving MYC, BCL2 and BCL6 genes by FISH in a retrospective, single-center series of large B-cell lymphomas, in order to allow a better classifications of these cases according to the current WHO 2017 classification. If this evaluation will be confirmed as a reliable method to reclassify in different groups the evaluated tumors, it can be subsequently

routinely apply to indicate the best treatment approaches in this high-risk setting of patients with a significant impact on patients' morbidity and mortality, and also on the health system and related costs. Moreover, this study could give important information about the real incidence and predictive value of MYC, BCL2 and BCL6 rearrangements.

OBJECTIVES

Primary objectives:

1. To re-classify retrospective series of large B-cell lymphomas (LBCL) according to the current WHO 2017 classification by using FISH for the detection of MYC, BCL2 and BCL6 rearrangements.
2. To establish the association between re-classification of LBCL using FISH for the detection of MYC, BCL2 and BCL6 rearrangements and survival.

Secondary objectives:

1. To establish the association between re-classification of LBCL using FISH for the detection of MYC, BCL2 and BCL6 rearrangements and patients' response to treatments.
2. To establish the association between re-classification of LBCL and risk of relapse.
3. To demonstrate that re-classification of LBCL exploiting FISH for the detection of MYC, BCL2 and BCL6 rearrangements is a reliable tool to support treatment decision plan.
4. To complete IHC analysis for further and/or novel pattern of antigen expression in HGBL.
5. To estimate the prevalence of MYC, BCL2 and BCL6 rearrangements/amplifications detected by FISH in LBCL
6. To describe the main treatment patterns according to disease characteristics.

THERAPEUTIC OUTCOME

Primary outcome:

1. Overall Survival (OS)

Secondary outcome:

1. Progression-free Survival (PFS)
2. Overall Response Rate (ORR; partial response [PR] + complete remission [CR])
3. Duration of response (DOR; partial response [PR] + complete remission [CR])
4. Relapse rates and patterns
5. Incidence of MYC, BCL2 and BCL6 rearrangements in LBCL

STUDY DESIGN

Single center, retrospective observational, pharmacological and of molecular characterization study.

Study duration 1 year

STUDY POPULATION

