Adult subjects (> 18 years old) of any age and gender affected by large B-cell lymphomas.

Inclusion Criteria:

- Histologically-confirmed diagnosis of LBCL (i.e., DLBCL, HGBCL, unclassifiable B-cell lymphoma with features intermediate between DLBCL and BL), or aggressive B-cell lymphomas with blastoid morphology (excluding blastoid variant of mantle cell lymphoma and lymphoblastic lymphoma)
- Histopathological diagnosis performed between 2000 and 2019.
- HIV sero-negativity
- Age ≥ 18
- Treatment with R-CHOP or other intensified polychemotherapy regimen
- Availability of adequate histopathological samples at diagnosis for FISH analysis
- Availability of clinical records and outcomes data

Exclusion criteria

- Histologic diagnosis other than DLBCL or unclassifiable B-cell lymphoma with features intermediate between DLBCL and BL

METHODS

Diagnostic tissue samples of patients who fulfil selection criteria for enrolment into the study will undergo local histopathological revision and analysis of chromosomal rearrangements involving MYC, BCL2 and BCL6 genes by FISH. Moreover, completion of IHC analysis for further and/or novel pattern of antigen expression in HGBL will be performed.

Treatments: anthracycline-based combinations followed or not by involved-field radiotherapy

Assignment of Subject Identification

The participants will be assigned a unique trial specific number and will henceforth be identified by that number in the database.

Data Collection

The data of all patients enrolled in the study will be collected from clinical folders and source documents (e.g., hospital records; clinical and office charts; laboratory notes etc.) and registered in the database as described in the following paragraphs.

Histopathology and Immunohistochemistry

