Clinical characteristics and response rates of the therapeutic subgroups will be compared using the α_2 test or Fisher exact test for categorical variables, according to the sample size. Factors potentially conditioning outcome will be assessed by α_2 test and logistic regression. Survival curves will be generated by the Kaplan-Meier method. Overall survival (OS) will be calculated from the date of pathologic diagnosis to death or to the last date of follow-up, while progression-free survival (PFS) will be calculated from the first day of treatment to relapse, progression or death, or to the last date of follow-up. Survival rates will be reported as 2-year OS and 95% CI. Impact on survival of clinical and therapeutic variables will be evaluated by comparing the entire OS curves by means of the log-rank test.

The independent prognostic value of variables will be analyzed using the Cox model. The year of diagnosis will be included as a continuous variable in the multivariate analyses to exclude the possibility that modern medical management could influence outcome more than the treatment itself. Backward stepwise regression will be performed to identify the most powerful predictors of survival. All the probability values will be two-sided. Statistical analysis will be performed with Statistical software (Statistica 10.0, Tuxon, AZ, USA) on a unique database including clinical and pathological data on an estimated sample size of 555 patients.

ETHICAL CONSIDERATIONS AND INFORMED CONSENT

The Investigator and all study staff will ensure that the clinical study is conducted in accordance with good clinical practice and institutional requirements, including those for subject privacy, Ethics Committee approval and record retention, and with the Declaration of Helsinki (revised October 2008) and in compliance with principles defined in the Determinazione of the Agenzia Italiana del Farmaco, dated 20 March 2008. The protocol, being retrospective, will be notified to the IEC of the IRCCS San Raffaele Scientific Institute

of Milan. In the context of clinical practice, patients already provided consent to use of health data for research purposes.

PATIENT SAFETY

Given the observational retrospective nature of the study, for the patients enrolled in this study, there are no additional physical, psychological, or social adverse effects compared to the standard of care clinical practice.

FINANCE AND INSURANCE

The study is non-profit in nature.

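### OS is counted from diagnosis in a cohort selected on having been treated, so early deaths are depleted and 2-year OS is biased modestly upward

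*Protocol*

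**What the plan says.** The section Statistical Considerations and Analysis Plan fixes the origin of the primary outcome: "Overall survival (OS) will be calculated from the date of pathologic diagnosis to death or to the last date of follow-up". The same sentence goes on to say that "progression-free survival (PFS) will be calculated from the first day of treatment to relapse, progression or death". On estimation and testing it says "Survival curves will be generated by the Kaplan-Meier method", "Survival rates will be reported as 2-year OS and 95% CI", and that variables will be assessed by "comparing the entire OS curves by means of the log-rank test", followed by a Cox model. None of these statements mentions delayed entry, left truncation or a landmark.

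The Inclusion Criteria, in the synopsis and again under Study Population, require "Treatment with R-CHOP or other intensified polychemotherapy regimen". The Methods section describes the treatments covered: "Treatments: anthracycline-based combinations followed or not by involved-field radiotherapy".

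The Therapeutic Outcome section names OS as the only primary outcome. The Objectives section in the body makes the association of FISH re-classification with survival a primary objective.

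**The concern.** Eligibility depends on an event after the OS clock has started. A patient who died after biopsy but before chemotherapy cannot meet the treatment criterion and is absent from the cohort. The patients who remain are nevertheless counted as at risk from the date of biopsy. Between diagnosis and first treatment they add person-time to the denominator but could not have added a death. This is guaranteed (immortal) time created by the entry rule. It arises whichever variable is tested, and a larger sample does not remove it.

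What is at stake is the absolute level of 2-year OS overall and in each class. The absolute shift is larger where mortality is higher, which on the Background's account of standard treatment is HGBL. If the gap also differed between FISH classes, the class with the longer gap would receive more death-free time, and part of any survival difference would come from the clock rather than the disease.

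**Working it through.** The protocol gives no figure that depends on the OS origin, so there is nothing of its own to reproduce. The check sizes the shift.

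**Inputs from the protocol (Background).**
- Scenario A: median OS for HGBL under standard treatment of 12 months or less; 12 is used.
- Scenario B: 5-year OS of 66% among the HGBL patients in the retrospective series of the intensified regimen.

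**Assumptions, not in the protocol.**
- Survival is exponential and counted from treatment. The Background does not state the origin of either figure.
- The hazard before treatment equals the hazard afterwards. A higher pre-treatment hazard would make the bias larger, a lower one smaller.
- The gap g between diagnosis and treatment is 2 to 12 weeks, at 4.345 weeks per month.

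**Formulae.** Monthly hazard λ is ln 2 / 12 = 0.05776 in A and −ln(0.66) / 60 = 0.00693 in B. Two-year OS from treatment is S(24) = exp(−24λ). On the diagnosis clock, with nobody able to die during g, the figure read at 24 months is S(24 − g). The ratio of the two is exp(λg), so the shift is always upward.

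**Results.**

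| Gap (assumed) | A: read from diagnosis | A: shift | B: read from diagnosis | B: shift |
|---|---|---|---|---|
| none | 25.0% | – | 84.7% | – |
| 2 weeks | 25.7% | +0.7 | 85.0% | +0.3 |
| 4 weeks | 26.4% | +1.4 | 85.2% | +0.5 |
| 8 weeks | 27.8% | +2.8 | 85.8% | +1.1 |
| 12 weeks | 29.3% | +4.3 | 86.3% | +1.6 |

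For example, 4 weeks is 4 / 4.345 = 0.92 months, and exp(−0.05776 × 23.08) = 0.2637. Median OS moves by the length of the gap.

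**Variable gap.** With a gamma-distributed gap (shape 2, mean 4 weeks), 2-year OS is again 26.4% in A and 85.2% in B. Recorded deaths in the first month after diagnosis fall from 5.6% to 1.7% in A and from 0.7% to 0.2% in B. Early deaths are thinned out but do not vanish.

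**Comparison of classes.** A log-rank test was simulated with 555 patients, an assumed HGBL share of 5, 10 or 15%, equal true hazards, assumed uniform censoring at 24 to 120 months, rejection at |Z| > 1.96, and 2,000 runs per setting (Monte Carlo standard error about 0.5 points).

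| Gap, HGBL vs other | A: false positives | B: false positives |
|---|---|---|
| 4 vs 4 weeks | 5.2–5.6% | 5.0–5.1% |
| 1 vs 4 weeks | 6.8% | 5.0–6.1% |
| 2 vs 6 weeks | 7.9–8.7% | 4.5–6.5% |

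Equal gaps leave the test near its nominal level. Unequal gaps inflate it in A, but A here gives all 555 patients the 12-month median, which the Background attaches only to HGBL. In B the rates stay close to nominal.

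**The case against.** **Diagnosis is a defensible origin.** FISH class is measured on the diagnostic specimen and is used to re-classify the diagnosis, so starting the clock at that specimen suits the prognostic question. Moving OS to treatment start changes the quantity estimated and does not recover patients who died untreated. This stands as an argument about which origin to choose. It does not justify uncorrected Kaplan-Meier on a treatment-selected cohort, because delayed entry keeps the diagnosis origin and removes the guaranteed time.

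**The shift is small against sampling error.** At 25% OS, with 28 to 83 HGBL patients (5 to 15% of 555, an assumed share) and censoring ignored, the 95% half-width is 1.96 × √(0.25 × 0.75 / n), or about 16 to 9 points. For the whole cohort at 85% it is 1.96 × √(0.85 × 0.15 / 555), about 3 points. This also stands, and it limits the weight of the point. The shift is systematic, however, and the confidence interval does not reflect it.

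**Stronger readings the text does not support.**
- A reader might infer that every OS curve has a stretch in which nobody can die. The guaranteed interval is specific to each patient. A curve is strictly flat only up to the shortest gap in its group; beyond that, deaths are depleted, not impossible.
- A reader might treat the different origins of OS and PFS as a contradiction, or expect the distance between the two curves to be misread. Both origins are stated openly in one sentence, and no contrast of OS with PFS is planned.
- A reader might conclude that the FISH-class comparison is invalid. That requires gaps that differ by class, and the protocol gives no gaps at all.
- The criterion does not say first-line. That reading is inferred from the requirement for samples at diagnosis and from the treatment list. If a later line could qualify, the guaranteed interval would be longer.

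**Conclusion.** The point holds. The entry criterion and the OS origin, both fixed in the protocol, together produce guaranteed-survival time in the primary outcome, and the stated methods do not adjust for it. Two-year OS is biased upward by about 1.4 to 2.8 points (12-month median) or 0.5 to 1.1 points (66% at 5 years) for gaps of 4 to 8 weeks. These figures rest on assumed gap lengths, exponential survival from treatment, and equal hazards before and after treatment start. Distortion of the primary comparison between FISH classes is conditional on unequal gaps and has not been shown. This is a modest bias in one direction that is cheap to remove; it does not undermine the study.

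**What to change.** Adopt one of two definitions in the statistical section:

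1. Start OS at the first day of treatment, the origin already used for PFS.
2. Keep OS from pathologic diagnosis, with each patient entering the risk set at the first day of treatment (left truncation) in the Kaplan-Meier, log-rank and Cox analyses.

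Under either definition, report the diagnosis-to-treatment interval by FISH class, so that readers can see whether the comparison of classes could be affected.

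The cost is a sentence or two of text. The treatment start date is already needed for PFS, so no extra data collection follows. OS figures will be slightly less favourable. The first option is less directly comparable with series counted from diagnosis. The second has few patients at risk at the very start of the curve and assumes that, at a given time since diagnosis, patients already treated represent those still waiting. Neither option brings back patients who died untreated, so the results describe treated patients only and should be labelled accordingly.

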intensified chemo-immunotherapy approaches has been investigated. Promising results emerged when treating patients with R-DA-EPOCH regimen, together with adequate CNS prophylaxis. [Petricch AM, Blood 2014]. Excellent efficacy and safety results were also reported in a multicenter phase II trial addressing a dose-dense, short-term therapy in HIV-positive patients diagnosed with high-risk BL or HGBL with MYC rearrangements [Ferreri et al. BJH 2021]. In the last decades, the “CARMEN” regimen was adopted at our institution and at several Italian Centers also for the treatment of HIV-negative patients diagnosed with high-risk DLBCL as well as B-cell lymphoma unclassifiable with features intermediate between DLBCL and BL with alterations of c-MYC. A retrospective series of 63 HIV-negative and –positive patients (22 HGBL) confirmed good tolerability and efficacy: after induction, 18 (82%) HGBL patients achieved a response, which was CR in 10 (45%) patients. At a median follow-up of 54 (2-131) months, the 5-year PFS and OS among HGBL were 67% and 66%, respectively. HIV seropositivity did not modify outcome.

Although FISH represents the gold standard for detection of MYC, BCL2 and BCL6 rearrangements, it is not routinely recommended in all cases at diagnosis. Indeed, a consensus has not yet been reached to provide specific guidelines as to which LBCL should be evaluated. Some believe that all DLBCL should have genetic studies for the detection of the three genes rearrangements, whereas others would limit them, for example, to cases with a GCB phenotype and/or high-grade morphology or to cases with >40% MYC+ cells in immunohistochemistry (IHC). In particular, at our institution, FISH for MYC is considered when MYC expression by IHC is >40%, and FISH for BCL-2 and BCL-6 are performed only when FISH for MYC is positive. However, since the presence MYC and BCL2 and/or BCL6 rearrangements is not invariably associated with IHC overexpression, the current diagnostic approach could have underestimated the real incidence of HGBL leading to the undertreatment of these patients.

RATIONALE

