All relevant data collected during the study for all of the patients enrolled in the study shall be entered in a database (password protected excel) from source documents (e.g., hospital records; clinical and office charts; laboratory notes etc.) by the responsible investigator or someone authorized by the investigator in a timely manner (as soon as possible after the information is collected) to ensure that they are clear, complete and correct.

On all trial-specific documents, other than the signed consent, the participant will be referred to by the trial participant number/code, not by name.

The investigator shall arrange for the retention of patient files, other source data, and the Trial Master File for at least 7 years after the completion or discontinuation of the study.

Data Protection

The confidentiality of participant data, including, but not limited to forms, records and samples and participant privacy will be maintained according to the GDPR (UE) 2016/679.

The trial staff will ensure that the participants' anonymity is maintained. The participants will be identified only by initials and a Patient ID number on the ICF and the electronic database.

All documents will be stored securely and only accessible by trial staff and authorized personnel.

Data anonymization

Since this is a retrospective study without ad hoc informed consent, in order to ensure anonymity, the following procedure will be followed for all data of all subjects:

the assigned patient ID will not be related to the identification code present in the patient's clinical material; this will be guaranteed with the following procedures:

- A patient code will be associated with the clinical material (nominal);

- The code will be transcribed in a second document and associated with a second code obtained by randomization (called "Patient ID");
- The patient ID will then be reported in the CRF and the intermediate document will be destroyed at termination of data collection.

At the end of this process and in the continuation of the study, patient data will be treated completely anonymously.

STATISTICAL CONSIDERATIONS AND ANALYSIS PLAN

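### The log-rank rule for therapeutic variables, with OS counted from diagnosis, gives immortal-time bias if post-chemotherapy radiotherapy is tested as ever versus never

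*Protocol*

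**What the plan says.** Under Statistical Considerations and Analysis Plan, the protocol fixes the time origin: "Overall survival (OS) will be calculated from the date of pathologic diagnosis to death or to the last date of follow-up". The same section fixes the univariable test: "Impact on survival of clinical and therapeutic variables will be evaluated by comparing the entire OS curves by means of the log-rank test". A Cox model follows, and then "Backward stepwise regression will be performed to identify the most powerful predictors of survival". No landmark, delayed entry or time-dependent coding is mentioned for either step.

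Two places describe treatment. The inclusion criteria require "Treatment with R-CHOP or other intensified polychemotherapy regimen". The Methods section adds "Treatments: anthracycline-based combinations followed or not by involved-field radiotherapy". Study Variables lists therapeutic management among the items to be considered. The treatment objective itself is descriptive: "To describe the main treatment patterns according to disease characteristics".

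Under Data anonymization, a document connects the clinical material to the study's patient ID. The protocol states that "the intermediate document will be destroyed at termination of data collection".

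**The concern.** An ordinary log-rank test on whole curves gives each patient one group label from time zero. The first-line regimen can be labelled in that way. Radiotherapy cannot, because whether a patient receives it is settled only after chemotherapy, months after diagnosis. Under an ever/never label, nobody who dies during chemotherapy can belong to the radiotherapy group. The months before radiotherapy are therefore free of deaths by construction in one group, and every early death is charged to the other.

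This component always pushes towards apparent benefit of radiotherapy. Backward stepwise selection could then keep the artefact and report it as a predictor of survival. Adjusting for year of diagnosis, as the protocol plans, deals with calendar trends and not with this bias.

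Timing matters as well. Both remedies need the radiotherapy start date. Once the linking document is gone, a date that was not abstracted cannot be recovered, whatever a later analysis plan says.

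**Working it through.** The protocol gives no figure to reproduce here: it states no alpha, effect size or event count for this comparison. The check therefore asks what the stated rule returns when radiotherapy has no effect at all.

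**Inputs from the protocol**
- n = 555 (analysis section).
- OS from pathologic diagnosis; two-year OS is the reported rate (analysis section).
- Five-year OS of 66%. The Background reports "At a median follow-up of 54 (2-131) months, the 5-year PFS and OS among HGBL were 67% and 66%, respectively", from 22 HGBL patients. It is the only five-year OS given.

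**Assumptions**
- The 66% applies to the whole series; 50–80% is shown as a range.
- Constant hazard.
- Radiotherapy at months 4–8, in 20–40% of those still alive, allocated at random.
- Follow-up of 60 months, or uniform over 2–131 or 24–240 months.
- Two-sided 5% test.

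**Two-year OS in closed form.** Let λ = −ln(OS5)/60, t the radiotherapy month and q the uptake.
- Radiotherapy group: exp(−λ(24 − t)).
- No-radiotherapy group: (1 − q)·exp(−24λ) / (1 − q·exp(−λt)).

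With OS5 = 0.66, t = 6 and q = 0.30:
- λ = 0.4155/60 = 0.006925.
- Radiotherapy: exp(−0.006925 × 18) = 0.883.
- No radiotherapy: 0.70 × 0.8469 / (1 − 0.30 × 0.9593) = 0.5928/0.7122 = 0.832.

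Every patient has the same true two-year OS of 84.7%, yet the split shows 88% v 83%. The same formulas give 81% v 74% at five-year OS 50%, and 93.5% v 90.6% at 80%. Over months 4–8 and uptake 20–40%, the gap is 3.0–7.8 points (66%), 4.4–11.6 (50%) and 1.7–4.5 (80%).

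**Simulation, null effect, fixed radiotherapy month** (300,000 patients per setting for the hazard ratio (HR); 1,000 series of 555 per setting for the log-rank)

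| Five-year OS | Ever/never HR | Log-rank false positives |
|---|---|---|
| 80% | 0.78–0.95 | 5–23% |
| 66% | 0.76–0.94 | 6–38% |
| 50% | 0.75–0.93 | 7–66% |

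Across these settings, a landmark or a time-dependent covariate gives HR 0.98–1.03. The landmark test has 3–6% false positives.

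**Start dates spread over months 4–8 after treatment start, OS from diagnosis, 66% case**
- Ever/never: HR 0.82–0.91, false positives 8–28%.
- Time-dependent covariate: HR 1.00–1.01.
- Landmark at month 10: HR 0.99–1.01, false positives 4–6%.

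**Confounding.** This check adds a prognostic factor (HR 2, prevalence 50%) that shifts radiotherapy uptake to 40% v 20%.

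| Model | Better-risk irradiated more | Worse-risk irradiated more |
|---|---|---|
| Ever/never | 0.72 | 0.98 |
| Time-dependent | 0.84 | 1.17 |
| Time-dependent plus the factor | 0.99 | 1.00 |

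**Effect on FISH class.** The Background's median OS of 12 months for HGBL on standard treatment, set against 66% at five years, implies an HR of (ln 2/12)/0.006925 = 8.34. Adding ever/never radiotherapy to a Cox model simulated at that HR moves the FISH estimate from 8.37 to 8.33. At an assumed FISH HR of 2–3 it moves by 0.01 or less.

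**The case against.** The strongest reply is that the faulty test is not written down. The log-rank sentence speaks of therapeutic variables in general, no ever/never coding is stated, and radiotherapy appears only in a description of treatments. Coding of covariates is usually left to an analysis plan, and the Cox sentence is compatible with a time-dependent covariate. This is right as far as it goes, so the point is conditional on how radiotherapy is tested. It does not dispose of the point. The protocol itself fixes both the time origin and the test, without qualification, and radiotherapy is the one treatment it describes as following chemotherapy in only some patients. A risk-set version of the log-rank could handle updated status, but that is not a comparison of entire curves from diagnosis.

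It is also true that no listed objective depends on a radiotherapy effect. FISH class is determined on the diagnostic sample. First-line regimen is known at treatment start, and all included patients were treated. This limits the importance of the point and is accepted.

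Radiotherapy timing, uptake and follow-up are assumed. The 66% comes from a small series that included HIV-positive patients, whom this study does not include, although the Background reports that HIV status did not modify outcome. At the mild end the false-positive rate is about nominal. Confounding by selection can work either way, so the sign of the result actually observed cannot be predicted. All of that stands. Only the direction of the immortal-time component is certain.

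Finally, nothing says that radiotherapy dates will not be collected. Equally, nothing says that they will, and the omission could not be repaired once the link is destroyed.

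**Conclusion.** The concern holds, with limited reach. Applied as written to ever/never radiotherapy, the rule gives a comparison biased towards radiotherapy by its construction. In the 66% case the null HR appears as 0.76–0.94, with 6–38% false significance at n=555. Across five-year OS of 50–80% the ranges are 0.75–0.95 and 5–66%. These sizes rest on assumed radiotherapy timing and uptake, constant hazard, assumed follow-up, and the application of a figure from 22 HGBL patients to the whole series. The primary comparison of FISH class with OS, and that of first-line regimen with OS, are essentially unaffected. This should be corrected, but it does not undermine the study's main question.

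**What to change.** Keep the log-rank on the whole OS curves for variables known at treatment start. Add one sentence for radiotherapy and any other treatment whose status is settled later. It should specify either a time-dependent covariate in the Cox model, or a landmark at a prespecified time after induction with status fixed at that time. Keep the baseline prognostic variables in the same model, because either method removes immortal time but not confounding by selection.

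Add the radiotherapy start date to the data abstracted, and the end-of-induction date if the landmark needs it. Both must be collected before the linking document is destroyed.

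The cost is one sentence and one or two dates per patient, from records going back to 2000. A landmark at month 10 leaves out 6–11% of patients in the 66% case (3–15% over five-year OS of 50–80%), and its result applies only to those who reach it. The time-dependent covariate leaves out none.
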